## Physiologic Pacing Registry Clinical Plan

### Vulnerable Populations

Vulnerable populations will not be enrolled in the Physiologic Pacing Registry.

### 5.3 Eligibility Criteria

#### 5.3.1 General Eligibility Criteria

Assessment for general eligibility criteria is based on medical records of the site and interview with a candidate patient. If some of the clinical and laboratory tests are not included in the site's standard tests, they must be done after written informed consent is obtained. Patients must meet ALL the inclusion criteria to be considered for the registry. If ANY of the exclusion criteria are met, the patient is excluded from the registry and cannot be enrolled.

#### 5.3.2 Inclusion Criteria

##### 5.3.2.1 General Inclusion Criteria

Subjects must meet all the following inclusion criteria for enrollment in the registry.

1. Scheduled for implantation of an Abbott pacemaker, defibrillator, or CRT-P/D device with any commercially available pacing lead as part of a physiologic pacing procedure according to the clinical site's routine care.
2. At least 18 years of age.
3. Willing and able to comply with the prescribed follow-up tests and schedule of evaluations.
4. Provided written informed consent prior to any registry-related procedures.

#### 5.3.3 Exclusion Criteria

##### 5.3.3.1 General Exclusion Criteria

Subjects will be excluded from enrollment if any of the exclusion criteria is met below.

1. History of tricuspid valve repair or replacement.
2. Currently participating in another clinical study with an active treatment arm and belong to the active arm
3. Presence of other anatomic or comorbid conditions, or other medical, social, or psychological conditions that, in the investigator's opinion, could limit the subject's ability to participate in the registry or to comply with follow-up requirements, or impact the scientific soundness of the registry results.
4. Chronic physiologic pacing lead implanted
5. Life expectancy of < 6 months.
6. Known contraindication for physiologic pacing therapy/implant (i.e. ongoing infection, known occlusion of the subclavian vein, etc.).

### 5.4 Subject Enrollment

A patient is considered enrolled in the registry once he/she meets eligibility requirements and has signed the informed consent form. Subjects who have a successful implant and are later found to have met exclusion criteria

## Physiologic Pacing Registry Clinical Plan

or not all inclusion criteria will continue follow-up in the registry and will be included in the enrolled population; a protocol deviation will be completed for these subjects.

### 5.5 Subject Withdrawal

Each enrolled subject shall remain in the registry until completion of the required follow-up period; however, a subject's participation in any registry is voluntary and the subject has the right to withdraw at any time without penalty or loss of benefit. Conceivable reasons for discontinuation may include, but not be limited to, the following:

- Subject death
- Subject voluntary withdrawal
- Subject withdrawal by physician as clinically-indicated
- Subject lost-to follow-up as described below

The Sponsor must be notified of the reason(s) for subject discontinuation. The site will provide this information to the Sponsor. Investigators must also report this to their respective EC/IRB as defined by their institution's procedure(s). No additional follow-up will be required or data recorded from subjects once withdrawn from the registry. The status of the subject's condition should be documented at the time of withdrawal.

Before the subject is withdrawn from the registry the site should make attempts to schedule the subject for a final registry follow-up visit. At this final follow-up visit, the subject will undergo the following assessments with documentation completed on the unscheduled follow-up form:

- Follow-up related workflow
- Physiologic pacing capture and sensing thresholds
- For His placement only - Measured H wave using device IEGM
- Measured R wave using device IEGMs through the lead implanted for physiologic pacing
- QRS duration for all physiologic pacing captures observed using 12-lead ECG
- PR interval using 12-lead ECG
- Incidence of increase in capture threshold of  $> 1V$  in the lead implanted for physiologic pacing or RV pacing leads
- Far-field atrial oversensing and ventricular oversensing and/or any interventions – including programming – required to address these issues
- NYHA Classification
- LVEF, LVEDV, LVESV (if available)
- Tricuspid and mitral regurgitation severity by echocardiogram (if available)
- Device estimated battery longevity via device session records
- Frequency/burden of detected atrial and ventricular arrhythmias via device session records
- Procedure and device-related adverse events and device deficiencies

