#### 15.2 Risks Associated with Participation in this Clinical Registry

All procedures required by this registry are standard of care according to each individual clinical site's practice. There are no anticipated risks associated with participation in this registry or any risks beyond those identified in the individual device Indication for Use.

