2.8 Handling of Missing Data

All analyses will be based on available data with missing data excluded, unless otherwise stated.

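### Physician withdrawal on undefined clinical grounds ends all recording in a registry that assigns no treatment, so 6-month data and later events can be lost in a way related to outcome

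*Protocol*

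**What the plan says.** Protocol 5.5 starts from the rule that enrolled subjects stay until follow-up is complete. It then gives an open list of conceivable reasons for discontinuation, one of which is "Subject withdrawal by physician as clinically-indicated". No criteria follow. On what happens next it says "No additional follow-up will be required or data recorded from subjects once withdrawn from the registry". Section 7.3.1 makes withdrawal one of the points at which safety surveillance stops.

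Section 5.5 also contains three safeguards:
- "The Sponsor must be notified of the reason(s) for subject discontinuation".
- Sites are asked to write down how the subject was doing on leaving.
- "Before the subject is withdrawn from the registry the site should make attempts to schedule the subject for a final registry follow-up visit", covering nearly the full follow-up list, with "documentation completed on the unscheduled follow-up form".

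Protocol 3.0 describes the design as observational. Section 15.2 says the required procedures are standard care at each site and adds "There are no anticipated risks associated with participation in this registry".

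SAP 2.3.2 summarises follow-up descriptively at 1 and 6 months. SAP 2.8 states "All analyses will be based on available data with missing data excluded", subject to a proviso for anything stated otherwise. SAP 3.2 summarises adverse events over all enrolled subjects, and SAP 3.3 summarises reasons for early termination.

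**The concern.** In a trial that assigns treatment, a physician may need to take a subject off that treatment for safety. Here there is no assigned treatment to stop, so leaving the registry changes what is recorded and not the care given. An exit made on clinical grounds, by the physician who sees how the subject is doing, is the kind most likely to be related to outcome.

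If subjects who are doing badly leave more often, available-case summaries of 6-month thresholds, NYHA class and LVEF will look better than the full implanted cohort would. Adverse event percentages could be understated too, because a withdrawn subject stays in the all-enrolled denominator while later events are not collected. Kaplan-Meier estimates under SAP 2.2.3 censor at the last event-free time, and that censoring would be informative if withdrawal follows decline. If physicians who map with EnSite and those who do not use the clause differently, any follow-up comparison between them would carry the difference.

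**Working it through.** The plan states no withdrawal rate, outcome rate or power calculation, so there is no figure to reproduce. The check is mainly a reading, with an illustration of scale.

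**Can the data be lost under the visible text?**

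1. *Exit.* Physician withdrawal on clinical grounds is allowed without criteria (5.5). Failed implant, explant and no attempt have their own rules in 6.2.1, and the first two keep 30 days of adverse-event follow-up. The 5.5 bullet has no such tail.
2. *After exit.* Nothing further is recorded (5.5), and surveillance ends (7.3.1).
3. *At exit.* The final visit is to be attempted; it is not mandatory. Table 3 does not mark LVEF or the Section 6.3 follow-up data in its Unscheduled column, although 5.5 lists LVEF for this visit.
4. *Use of the final visit.* Taking a month as 30 days, the Table 2 windows are days 30 − 14 = 16 to 30 + 30 = 60, and days 180 − 60 = 120 to 180 + 60 = 240. A final visit on days 61 to 119 falls in neither. One on days 16 to 60 could serve only the 1-month summary. No visible text carries final-visit data into the 6-month results.
5. *Analysis.* SAP 2.3.2 and 2.8 then summarise those with data. No visible sensitivity analysis addresses withdrawals.

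By contrast, 5.4 keeps successfully implanted subjects in follow-up even when they are later found ineligible.

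**How large could it be?** All rates below are assumptions. The n of 1,000 is the enrolment maximum in SAP 1.3.

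*Bounds.* Let p be the poor-outcome rate among retained subjects, w the proportion withdrawn and q the rate among the withdrawn. The full-cohort rate is (1 − w)p + wq. With p = 10%:

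| w | q = 0% | q = 50% | q = 100% |
|---|---|---|---|
| 2% | 9.8% | 0.98 × 10% + 0.02 × 50% = 10.8% | 11.8% |
| 5% | 9.5% | 0.95 × 10% + 0.05 × 50% = 12.0% | 14.5% |
| 10% | 9.0% | 0.90 × 10% + 0.10 × 50% = 14.0% | 19.0% |

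*Selection on outcome.* Let the true rate be P = 10%, with withdrawal of 2% among subjects with a good outcome and b among those with a poor one. The observed rate is P(1 − b) / [P(1 − b) + (1 − P)(0.98)]. Per 1,000 subjects:
- b = 2%: 98/(98 + 882) = 10.0%, no bias.
- b = 10%: 90/(90 + 882) = 9.3%.
- b = 20%: 80/(80 + 882) = 8.3%.
- b = 30%: 70/(70 + 882) = 7.4%.

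*Scale.* The sampling half-width is 1.96 × √(0.1 × 0.9/1,000) = 1.86 points. The exact Clopper-Pearson interval for 100/1,000 is 8.2% to 12.0%. Under these assumptions the bias is smaller than sampling error at b = 20% (1.68 points) and larger at b = 30% (2.65 points).

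**The case against.** The strongest reply is that the plan is better protected than the bullet alone suggests. The sponsor must be told the reason, status should be documented (11.3 also asks for it in the source record), and the attempted final visit covers thresholds, NYHA class, LVEF if available and adverse events. Serious events, including deaths, and related events are collected up to withdrawal. A serious deterioration that prompts withdrawal is therefore already reportable and stays in the SAP 3.2 summary. All of this stands, and it confines the loss to 6-month visit data and events after withdrawal.

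A reader might also infer four stronger things that the documents do not support:

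- *The clause can only remove subjects because of their clinical course.* The list in 5.5 is open and the term undefined. The bullet may refer partly to the exits in 6.2.1, and a change of strategy involving explant is governed there. The text permits outcome-related withdrawal; it does not show that every use would be of that kind.
- *Final-visit data are excluded because of the form used.* No visible SAP text assigns data to visits by form, and a final visit may fall inside a window. The gap is that nothing says how such data are used.
- *SAP 3.3 leaves physician withdrawal out.* Its list is open-ended, so the category can be reported. It is merely not named.
- *The planned EnSite comparison is biased.* The visible subgroup analysis (SAP 2.7) covers major implant characteristics, recorded before follow-up dropout can occur. Only a follow-up comparison is exposed. That is a stated objective (Protocol 2.1.1, SAP 1.2), but no visible section specifies its analysis.

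Finally, Protocol 8.2.1 and 8.8 and SAP 2.5 and 2.6 are redacted and may hold further handling. That is not counted against the plan.

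**Conclusion.** The point holds as a gap in retention. The stated rules allow a subject to leave on undefined clinical grounds and end all recording at that moment, and no visible text repairs the resulting loss. The existing safeguards reduce it without removing it.

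The documents show that outcome-related loss can happen, not that it will or how often. If withdrawal is unrelated to outcome, the bias is zero. With a few per cent withdrawn and a 10% poor-outcome rate, plausible distortion runs from under one point to a few points, which is comparable with sampling error at 1,000 subjects. With fewer 6-month observations the sampling error is wider and the bias relatively smaller. The registry is descriptive and tests no hypothesis, so what is at stake is the accuracy of its 6-month description and late safety figures. This is a worthwhile, cheap improvement to the plan.

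**What to change.** Amend the sentence in Protocol 5.5 that ends recording at withdrawal, and the matching end of surveillance in 7.3.1. Physician withdrawal should end registry-specific visits only. Adverse events, vital status, lead and device status, and routine device session records should continue to be taken from the chart to the 6-month window, unless the subject withdraws consent. Name physician withdrawal as its own early-termination category in SAP 3.3, tabulated by EnSite use.

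Deleting the bullet would not be enough: the list is open, so removing one item forbids nothing, and the sentence that stops recording would remain.

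The cost is a wording amendment, handled through the ethics committee process in 10.2, and a short chart-based form for a few subjects. Section 11.4 already bases primary data collection on chart review, so no new data source is needed. Patient care and the right to withdraw consent are unchanged.

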#### Lost-to-Follow-up

If the subject misses the scheduled 1-month follow-up time point and the attempts at contacting the subject detailed below are unsuccessful, then the subject is considered lost-to-follow-up. Site personnel shall make all reasonable

## Physiologic Pacing Registry Clinical Plan

efforts to locate and communicate with the subject (and document these efforts in the source documents), including the following, at each contact time point:

- A minimum of two telephone calls on different days over the specified follow-up windows to contact the subject should be recorded in the source documentation, including date, time and initials of site personnel trying to make contact.
- If these attempts are unsuccessful, a letter (certified if applicable) should be sent to the subject.
- If a subject misses the 1-month follow-up contact time point, it will be considered a missed visit. The subject may then return for the 6-month follow-up visit. If the subject misses the 1-month follow-up visit and the above-mentioned attempts at communicating with the subject are unsuccessful, the subject will be considered lost-to-follow-up.

**Note:** Telephone contact with a General Practitioner, non-registry Cardiologist or relative without the presence of the subject or indirect documentation obtained via discharge letters will not be considered as subject contact.

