**Table 2: Registry Time Interval Windows**

1 Month	6 Months
-14 days/+30 days	± 60 days

Sites will follow all subjects at 1 month and 6 months after the date of successful HBP lead and Abbott device implant.

During each follow-up visit, the following data will be collected:

- Follow-up related workflow
- Physiologic pacing capture and sensing thresholds
- For His placement only: Measured H wave using device IEGM
- Measured R wave using device IEGMs through lead implanted for physiologic pacing
- Presenting QRS duration and PR interval from 12-lead ECG
- QRS duration for all types of physiologic pacing captures observed from 12-lead ECG
- Incidence of increase in capture threshold of > 1V in leads implanted for physiologic or RV pacing leads
- Far-field atrial oversensing and ventricular oversensing and/or any interventions – including programming – required to address these issues
- NYHA Classification
- LVEF, LVEDV, LVESV (if available)
- Tricuspid and mitral regurgitation severity by echocardiogram (if available)
- Device estimated battery longevity via device session records
- Frequency/burden of detected atrial and ventricular arrhythmias via device session records
- Procedure and device-related adverse events and device deficiencies

Sites must download the device session records and submit to Abbott using the EDC system. Sites must also submit copies of the subject's physiologic pacing 12-lead ECGs in digital format (if available). Sites must complete and submit the associated Follow-up visit CRFs to Abbott using the EDC system.

Sponsor Representatives may provide support during the follow-up procedures for device-related data collection.

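### Protocol section 5.5 allows a subject to be declared lost to follow-up on 1-month non-contact alone, before the 6-month window opens

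*Protocol*

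**What the plan says.** The lost-to-follow-up part of protocol section 5.5 states its trigger twice. The opening sentence reads "If the subject misses the scheduled 1-month follow-up time point and the attempts at contacting the subject detailed below are unsuccessful", and the consequence is lost-to-follow-up status. The last bullet repeats it: "If the subject misses the 1-month follow-up visit and the above-mentioned attempts at communicating with the subject are unsuccessful, the subject will be considered lost-to-follow-up". Both name only the 1-month visit.

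That same bullet first says "If a subject misses the 1-month follow-up contact time point, it will be considered a missed visit", and then "The subject may then return for the 6-month follow-up visit".

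The contact effort is "A minimum of two telephone calls on different days over the specified follow-up windows to contact the subject", followed by a letter if the calls fail. The section asks for these efforts at every contact time point. A note adds that reaching a relative, a general practitioner or an outside cardiologist without the subject, or holding a discharge letter, does not count as contact.

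Earlier in 5.5, loss to follow-up appears among the possible reasons for discontinuation, and the plan says "No additional follow-up will be required or data recorded from subjects once withdrawn from the registry". The default in 5.5 is that subjects stay in until their follow-up is complete.

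Other relevant provisions:
- Protocol 7.3.1 ends safety surveillance at the last visit, death, conclusion of participation or withdrawal.
- SAP 3.3 counts loss to follow-up as early termination.
- SAP 2.3.2 summarises follow-up characteristics at 1 and 6 months, and SAP 2.8 uses available data only.
- SAP 2.2.3 censors event-free subjects at the last time they were known to be event-free.

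**The concern.** Loss to follow-up is normally settled when the last scheduled visit can no longer happen. Here it is settled at the first of two visits. A subject who is away or unresponsive around month 1 may still come to the site for a device check around month 6. By then the registry may already have closed that subject out, and the plan does not say whether data may be recorded. There is also no lost-to-follow-up rule for a missed 6-month visit.

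Such a subject has already missed month 1, so losing month 6 as well leaves no scheduled post-implant data. Protocol 1.1.1 and 1.1.2 name threshold stability over time and lead dislodgement as open problems, and the 6-month visit is the registry's later look at them. If early non-attenders differ from the rest, available-case summaries at 6 months are selected and late events are under-counted. The documents do not show that they differ, but nothing in the SAP would correct for it. The note excluding indirect contact adds to the worry: a subject known through a relative or a discharge letter to be in hospital can still be declared lost at month 1.

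**Working it through.** The plan states no dropout rate, and SAP 2.4 says there is no hypothesis test and no sample size calculation. There is therefore no figure to reproduce. The check is a day count, a reading of the rule and an illustration.

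**Day count.** The inputs are the Table 2 windows: 1 month -14/+30 days, 6 months ±60 days. Assumption: 1 month = day 30 and 6 months = day 180 after successful implant.
- 1-month window: 30 - 14 = day 16 to 30 + 30 = day 60.
- 6-month window: 180 - 60 = day 120 to 180 + 60 = day 240.
- From close of month 1 to opening of month 6: 120 - 60 = 60 days.
- From close of month 1 to the nominal 6-month visit: 180 - 60 = 120 days.
- From close of month 1 to close of month 6: 240 - 60 = 180 days.

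With an average month of 30.4375 days, the 60-day and 180-day gaps become 62.2 and 182.2 days. Day 60 is approximate, because the letter step carries no date.

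**What happens to each subject under the text.**

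| Situation at month 1 | What 5.5 says | At month 6 |
|---|---|---|
| Visit missed, subject reached | Missed visit | May return |
| Visit missed, subject not reached | Lost to follow-up, which is a discontinuation reason | No provision for return or reinstatement |
| Month-6 visit missed | No lost-to-follow-up rule | Not applicable |

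The second row is the problem. The step from that status to no data being recorded follows from combining parts of 5.5. No single sentence states it.

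**Number affected.** Formula: N × u × r, where N is subjects, u the share unreachable at month 1, and r the share of those who reappear at 6 months. N = 1,000 is the enrolment ceiling in SAP 1.3. The documents give neither u nor r, so both are assumed.
- Low: 1,000 × 0.01 × 0.25 = 2.5, about 3.
- Middle: 1,000 × 0.05 × 0.50 = 25.
- High: 1,000 × 0.10 × 0.75 = 75.

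**Precision.** Take u = 10% with half of those recovered, so n rises from 900 to 950. The approximate 95% half-width is 1.96 × √(p(1-p)/n).
- p = 5%: 1.42 percentage points at n = 900, 1.39 at n = 950.
- p = 50%: 3.27 percentage points at n = 900, 3.18 at n = 950.

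Precision hardly changes. What matters is who is missing.

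**The case against.** The strongest reply is that the text is coherent. A subject who misses month 1 but is reached may return, and one who misses and cannot be reached is lost. The second case is simply narrower. This reading is available and it stands. A reader might infer that 5.5 flatly contradicts itself by both closing out and readmitting the same subject. The documents do not support that, because the permission to return is not expressly given to the unreached subject. The harmonised reading leaves the early trigger in place, however.

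A second reply is that being considered lost is not the same as being withdrawn. Section 5.5 sets no close-out date, keeps subjects in by default, and asks sites to try for a final visit before withdrawal. It is right that immediate withdrawal is implied and not stated. A final visit does not help with someone who cannot be reached. A reader might also infer that data are discarded. They are not: nothing already collected is deleted, and the loss is of 6-month data that would not be collected.

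Third, contact efforts are already required at each time point, over follow-up windows in the plural, so the attempts could be read as spanning both visits. That is fair on the workload, but both trigger sentences name only the 1-month visit.

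Fourth, a reader might count every unreached subject as lost to safety surveillance because of this rule. That overstates it. Section 7.3.1 does not name loss to follow-up, and a site cannot collect events from someone it never reaches again. The rule costs event data only for those who reappear.

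Finally, 1,000 is a ceiling on enrolment, while visits run from successful implant, so the true base is smaller. Available-case analysis would be exposed to non-random loss under any rule, and the added effect of this one is unknown.

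**Conclusion.** The concern holds as a premature trigger combined with an ambiguity. Followed as written, 5.5 can end a subject's participation about 60 days before the 6-month window opens, with no route back and no rule for the 6-month visit itself. This rests on treating lost-to-follow-up status as withdrawal, which 5.5 and SAP 3.3 together imply but do not state.

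The size is unknown. The illustration of about 3 to 75 subjects (0.3% to 7.5% of 1,000) depends wholly on the assumed rates. The effect is confined to descriptive 6-month summaries, event counts and the early-termination tally. No test, power statement or sample size is touched. The change is worth making because the loss is avoidable and may not be random.

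**What to change.** Amend protocol 5.5 in both places where the trigger appears:
- A subject unreached at month 1 is recorded as a missed visit and stays enrolled.
- The calls and letter already required at each time point are made in the 6-month window.
- Lost-to-follow-up is assigned only when that window closes (6 months + 60 days) without a visit or contact.

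This also supplies the missing rule for the 6-month visit, and a subject who reappears within the window needs no reinstatement.

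The cost is a short amendment. Protocol 10.2 requires written ethics committee or IRB acknowledgement or approval before it takes effect, at up to 75 centres. Sites would keep status open up to about 180 days longer for a small number of subjects. The second round of contact attempts is largely work that the plan already asks for, and no new procedure is added.
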